5.2 Trial Treatment(s)

The treatment to be used in this trial is outlined below in [Table 2](#).

Table 2 Trial Treatment

Study Drug	Dose/Potency	Dose Frequency	Route of Administration	Regimen/Treatment Period	Use
pembrolizumab	200 mg	Q3W	IV infusion	Day 1 of each treatment cycle up to 35 administrations (approximately 2 years)	Experimental

Abbreviations: IV – intravenous; Q3W – every 3 weeks

Trial treatment should begin on the day of treatment allocation or as close as possible to the date on which the subject is allocated/assigned to treatment on the study.

The investigator shall take responsibility for and shall take all steps to maintain appropriate records and ensure appropriate supply, storage, handling, distribution and usage of trial treatments in accordance with the protocol and any applicable laws and regulations.

5.2.1 Dose Selection/Modification

5.2.1.1 Dose Selection (Preparation)

The rationale for selection of doses to be used in this trial is provided in Section 4.0 – Background and Rationale.

All subjects will receive 200 mg pembrolizumab by IV infusion within a 30 minute period, Q3W. Details on the preparation and administration of study drug are provided in the Pharmacy Manual.

5.2.1.2 Dose Modification

Adverse events (both nonserious and serious) associated with pembrolizumab exposure may have an immunologic etiology. These AEs may occur shortly after the first dose or several months after the last dose of treatment. Pembrolizumab must be withheld for drug related toxicities and severe or life-threatening AEs as per [Table 3](#).

In addition, subjects should receive appropriate supportive care measures as deemed necessary by the treating investigator. Suggested supportive care measures, as described in Section 5.6.1, are also included in [Table 3](#).

Dosing interruptions are permitted in the case of medical/surgical events or logistical reasons not related to trial therapy (e.g., elective surgery, unrelated medical events, subject vacation, and/or holidays). Subjects should be placed back on trial therapy within 3 weeks of the scheduled interruption, unless otherwise discussed with the Sponsor. The reason for interruption should be documented in the subject's trial record.

Table 3 Dose Modification and Toxicity Management Guidelines for Immune-Related Adverse Events Associated With Pembrolizumab

General instructions:				

 1. Corticosteroid taper should be initiated upon AE improving to Grade 1 or less and continue to taper over at least 4 weeks. 2. For situations where pembrolizumab has been withheld, pembrolizumab can be resumed after AE has been reduced to Grade 1 or 0 and corticosteroid has been tapered. Pembrolizumab should be permanently discontinued if AE does not resolve within 12 weeks of last dose or corticosteroids cannot be reduced to ≤ 10 mg prednisone or equivalent per day within 12 weeks. 3. For severe and life-threatening irAEs, IV corticosteroid should be initiated first followed by oral steroid. Other immunosuppressive treatment should be initiated if irAEs cannot be controlled by corticosteroids. 				
Immune-related AEs	Toxicity grade or conditions (CTCAEv4.0)	Action taken to pembrolizumab	irAE management with corticosteroid and/or other therapies	Monitor and follow-up
Pneumonitis	Grade 2	Withhold	
 • Administer corticosteroids (initial dose of 1-2 mg/kg prednisone or equivalent) followed by taper 	
 • Monitor participants for signs and symptoms of pneumonitis • Evaluate participants with suspected pneumonitis with radiographic imaging and initiate corticosteroid treatment • Add prophylactic antibiotics for opportunistic infections
	Grade 3 or 4, or recurrent Grade 2	Permanently discontinue		
Diarrhea / colitis	Grade 2 or 3	Withhold	
 • Administer corticosteroids (initial dose of 1-2 mg/kg prednisone or equivalent) followed by taper 	
 • Monitor participants for signs and symptoms of enterocolitis (i.e., diarrhea, abdominal pain, blood or mucus in stool with or without fever) and of bowel perforation (i.e., peritoneal signs and ileus). • Participants with \geq Grade 2 diarrhea suspecting colitis should consider GI consultation and performing endoscopy to rule out colitis. • Participants with diarrhea/colitis should be advised to drink liberal quantities of clear fluids. If sufficient oral fluid intake is not feasible, fluid and electrolytes should be substituted via IV infusion.
	Grade 4	Permanently discontinue		

Immune-related AEs	Toxicity grade or conditions (CTCAEv4.0)	Action taken to pembrolizumab	irAE management with corticosteroid and/or other therapies	Monitor and follow-up
AST / ALT elevation or increased bilirubin	Grade 2	Withhold	
 Administer corticosteroids (initial dose of 0.5- 1 mg/kg prednisone or equivalent) followed by taper 	
 Monitor with liver function tests (consider weekly or more frequently until liver enzyme value returned to baseline or is stable)
	Grade 3 or 4	Permanently discontinue	
 Administer corticosteroids (initial dose of 1-2 mg/kg prednisone or equivalent) followed by taper 	
Type 1 diabetes mellitus (T1DM) or Hyperglycemia	Newly onset T1DM or Grade 3 or 4 hyperglycemia associated with evidence of β -cell failure	Withhold	
 Initiate insulin replacement therapy for participants with T1DM Administer anti-hyperglycemic in participants with hyperglycemia 	
 Monitor participants for hyperglycemia or other signs and symptoms of diabetes.
Hypophysitis	Grade 2	Withhold	
 Administer corticosteroids and initiate hormonal replacements as clinically indicated. 	
 Monitor for signs and symptoms of hypophysitis (including hypopituitarism and adrenal insufficiency)
	Grade 3 or 4	Withhold or permanently discontinue ¹		
Hyperthyroidism	Grade 2	Continue	
 Treat with non-selective beta-blockers (e.g., propranolol) or thioamides as appropriate 	
 Monitor for signs and symptoms of thyroid disorders.
	Grade 3 or 4	Withhold or Permanently discontinue ¹		
Hypothyroidism	Grade 2-4	Continue	
 Initiate thyroid replacement hormones (e.g., levothyroxine or liothyronine) per standard of care 	
 Monitor for signs and symptoms of thyroid disorders.
Nephritis and renal dysfunction	Grade 2	Withhold	
 Administer corticosteroids (prednisone 1-2 mg/kg or equivalent) followed by taper. 	
 Monitor changes of renal function
	Grade 3 or 4	Permanently discontinue		

Immune-related AEs	Toxicity grade or conditions (CTCAEv4.0)	Action taken to pembrolizumab	irAE management with corticosteroid and/or other therapies	Monitor and follow-up
Myocarditis	Grade 1 or 2	Withhold	
 Based on severity of AE administer corticosteroids 	
 Ensure adequate evaluation to confirm etiology and/or exclude other causes
	Grade 3 or 4	Permanently discontinue		
All Other immune-related AEs	Intolerable/ persistent Grade 2	Withhold	
 Based on type and severity of AE administer corticosteroids 	
 Ensure adequate evaluation to confirm etiology and/or exclude other causes
	Grade 3	Withhold or discontinue based on the type of event. Events that require discontinuation include and not limited to: Guillain-Barre Syndrome, encephalitis		
	Grade 4 or recurrent Grade 3	Permanently discontinue		

Abbreviations: AE – adverse event; ALT – alanine transaminase; AST – aspartate transaminase; CTCAE – Common Terminology Criteria for Adverse Events; GI – gastrointestinal; irAE – immune-related adverse event; IV – intravenous; T1DM – type 2 diabetes mellitus.
 
1. Withhold or permanently discontinue pembrolizumab is at the discretion of the investigator or treating physician.
 
NOTE: For participants with Grade 3 or 4 immune-related endocrinopathy where withhold of pembrolizumab is required, pembrolizumab may be resumed when AE resolves to ≤ Grade 2 and is controlled with hormonal replacement therapy or achieved metabolic control (in case of T1DM).
				

5.2.2 Timing of Dose Administration

Trial treatment should be administered on Day 1 of each cycle after all procedures/assessments have been completed as detailed on the Trial Flow Chart (Section 6.0). Cycle 1 may not be administered until after completion of all screening assessments and randomization. Beginning with Cycle 2 trial treatment may be administered up to 3 days before or after the scheduled Day 1 of each cycle due to administrative reasons. Interruptions from the treatment plan for greater than 3 days and up to 3 weeks may be allowed, but require consultation between the investigator and Sponsor, and written documentation of the collaborative decision on subject management.

Trial treatments will be administered on an outpatient basis. Inpatient study drug administration may be allowed with sponsor consultation.

Pembrolizumab will be administered as a 30 minute IV infusion every 3 weeks. Sites should make every effort to target infusion timing to be as close to 30 minutes as possible. However, given the variability of infusion pumps from site to site, a window of -5 minutes and +10 minutes is permitted (i.e., infusion time is 30 minutes: -5 min/+10 min).

The Pharmacy Manual contains specific instructions for pembrolizumab reconstitution, preparation of the infusion fluid, and administration.

5.2.3 Extent of Trial Treatment

- All subjects may remain on treatment for up to 35 administrations of pembrolizumab (approximately 2 years) or until confirmed PD.
- Per the investigator's discretion subjects who achieve a CR may stop treatment and are eligible to restart treatment upon documented progression as long as they meet eligibility criteria specified in the protocol (see Section 7.1.5.2.1) and the trial is still ongoing. These subjects will be eligible for retreatment for up to 17 administrations of pembrolizumab (approximately 1 year).

5.2.4 Trial Blinding/Masking

This is an open-label trial; therefore, the Sponsor, investigator and subject will know the treatment administered.

5.3 Randomization or Treatment Allocation

Treatment allocation/randomization will occur centrally using an interactive voice response system / integrated web response system (IVRS/IWRS). There is one treatment arm.

Subjects participating in this trial will be allocated by non-random assignment.

5.4 Stratification

No stratification based on age, sex or other characteristics will be used in this trial.

5.5 Concomitant Medications/Vaccinations (Allowed & Prohibited)

Medications or vaccinations specifically prohibited in the exclusion criteria are not allowed during the ongoing trial. If there is a clinical indication for any medication or vaccination specifically prohibited during the trial, discontinuation from trial therapy or vaccination may be required. The investigator should discuss any questions regarding this with the Sponsor Clinical Director. The final decision on any supportive therapy or vaccination rests with the investigator and/or the subject's primary physician. However, the decision to continue the subject on trial therapy or vaccination schedule requires the mutual agreement of the investigator, the Sponsor and the subject.

5.5.1 Acceptable Concomitant Medications

All treatments that the investigator considers necessary for a subject's welfare may be administered at the discretion of the investigator in keeping with the community standards of medical care. All concomitant medication will be recorded on the case report form (CRF) including all prescription, over-the-counter (OTC), herbal supplements, and IV medications and fluids. If changes occur during the trial period, documentation of drug dosage, frequency, route, and date may also be included on the CRF. Subject may remain on anti-coagulation therapy as long as the prothrombin time or partial thromboplastin time is within therapeutic range of the intended use of anticoagulants

All concomitant medications received within 28 days before the first dose of trial treatment and 30 days after the last dose of trial treatment should be recorded. Concomitant medications administered after 30 days after the last dose of trial treatment should be recorded for SAEs and ECIs as defined in Section 7.2.

In subjects with rrRS, additional therapies to treat the underlying CLL (according to treatment guidelines) may be added at the physician's discretion if medically necessary and with Sponsor approval. These therapies must be approved by regulatory authorities for CLL and commercially available.

Corticosteroid use on study for management of AEs, SAEs, and ECIs, as a premedication for IV contrasts, allergies/reactions, or if considered necessary for a subject's welfare is allowed.

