Per the investigator's discretion subjects who attain a confirmed CR by independent central review may consider stopping trial treatment after receiving at least 8 administrations of pembrolizumab. At least two administrations of pembrolizumab must be received after CR is documented. These subjects will be eligible for retreatment for up to 17 administrations of pembrolizumab (approximately 1 year) after they have experienced disease progression at the discretion of the investigator if no cancer treatment was administered since the last dose of pembrolizumab, the subject still meets the safety parameters listed in the Inclusion/Exclusion criteria, and the trial remains open (see Section 7.1.5.2.1).

In subjects with rrRS, additional therapies to treat the underlying CLL (according to treatment guidelines) may be added (Section 5.5.1) at the physician's discretion if medically necessary and with Sponsor approval.

After the end of treatment, each subject will be followed for 30 days for AE monitoring (serious adverse events [SAEs] and events of clinical interest [ECIs] will be collected for 90 days after the end of treatment). Subjects who discontinue treatment for reasons other than disease progression will have post-treatment follow-up for disease status until disease progression, initiating a non-study cancer treatment, withdrawing consent, or becoming lost to follow-up. All subjects will be followed by telephone contact for OS until death, withdrawal of consent or the end of the study, whichever comes first.

The primary objective of the trial is to determine the objective response rate (ORR) as assessed by independent central review (utilizing the International Working Group [IWG] response assessment criteria per Cheson 2007 [1]) of pembrolizumab in subjects with relapsed or refractory PMBCL. For subjects with rrRS, IWG criteria with special considerations for RS will be used (Section 12.7).

Secondary objectives for each cohort include other efficacy parameters as progression free survival (PFS), OS, disease control rate (DCR), duration of response (DOR) and safety and tolerability. Analysis of programmed cell death ligand 1 (PD-L1) expression and corresponding efficacy; along with the relationship of candidate efficacy/resistance biomarkers and anti-tumor activity of pembrolizumab, and ORR utilizing the 5-point scale Lugano Classification (Section 12.8) will be investigated as exploratory objectives for each cohort.

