3.0 OBJECTIVE(S) & HYPOTHESIS(ES)

3.1 Primary Objective(s) & Hypothesis(es)

In subjects with rrPMBCL or rrRS:

1. **Objective:** rrPMBCL: Estimate the ORR of pembrolizumab by independent central review according to the IWG response criteria (Cheson, 2007 [1]).

Hypothesis: Intravenous (IV) administration of single agent pembrolizumab will result in an ORR of greater than 15% using IWG response criteria by independent central review.

2. **Objective:** rrRS: Estimate the ORR of pembrolizumab by independent central review according to the IWG response criteria (Cheson, 2007 [1]) with special considerations for RS (Section 12.7).

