5.5.2 Prohibited Concomitant Medications

Subjects are prohibited from receiving the following therapies during the Screening and Treatment Phase (including retreatment for post-complete response relapse) of this trial:

- Antineoplastic systemic chemotherapy or biological therapy
- Granulocyte Macrophage - Colony Stimulating Factor
- Immunotherapy not specified in this protocol, however Immunoglobulin Therapy (IVIG) is allowed
- Chemotherapy not specified in this protocol

- Investigational agents other than pembrolizumab
- Radiation therapy

Note: Radiation therapy to a symptomatic soft tissue lesion, bone lesions, or to the brain may be allowed after consultation with Sponsor.

Note: Radiation may be administered ONLY to subjects that have CR, PR, or SD who in the opinion of the investigator may have a tumor flare reaction in an isolated area. **Subjects that are progressing with no suspicion of tumor flare and require radiation therapy must be discontinued from study treatment.**

- Live vaccines within 30 days prior to the first dose of trial treatment and while participating in the trial. Examples of live vaccines include, but are not limited to, the following: measles, mumps, rubella, chickenpox, yellow fever, rabies, Bacillus Calmette-Guerin, and oral typhoid vaccine. Seasonal influenza vaccines for injection are generally killed virus vaccines and are allowed; however intranasal influenza vaccines (e.g., FluMist®) are live attenuated vaccines, and are not allowed.

Subjects who, in the assessment by the investigator and after consultation with the Sponsor, require the use of any of the aforementioned treatments for clinical management should be removed from the trial. Subjects may receive other medications that the investigator deems to be medically necessary.

The Exclusion Criteria describes other medications which are prohibited in this trial.

There are no prohibited therapies during the Post-Treatment Follow-up Phase. Subjects must be discontinued from the active follow-up phase if they begin a non-trial treatment for their underlying disease.

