5.8 Subject Withdrawal/Discontinuation Criteria

5.8.1 Discontinuation of Treatment

Discontinuation of treatment does not represent withdrawal from the trial.

As certain data on clinical events beyond treatment discontinuation are important to the study, they must be collected through the subject's last scheduled follow-up, even if the subject has discontinued treatment. Therefore, all subjects who discontinue trial treatment prior to completion of the treatment period will still continue to participate in the trial as specified in Section 6.0 - Trial Flow Chart and Section 7.1.5.3 – Post Treatment Visits.

Subjects may discontinue treatment at any time for any reason or be dropped from treatment at the discretion of the investigator should any untoward effect occur. In addition, a subject may be discontinued from treatment by the investigator or the Sponsor if treatment is inappropriate, the trial plan is violated, or for administrative and/or other safety reasons. Specific details regarding procedures to be performed at treatment discontinuation are provided in Section 7.1.4 – Other Procedures.

A subject must be discontinued from treatment but continue to be monitored in the trial for any of the following reasons:

- The subject or subject's legally acceptable representative requests to discontinue treatment.
 - Confirmed radiographic disease progression outlined in Section 7.1.2.7.5 (exception if the Sponsor approves treatment continuation).
 - Unacceptable adverse experiences as described in Section 7.2
 - Any progression or recurrence of any malignancy, or any occurrence of another malignancy that requires active treatment
 - Intercurrent illness other than another malignancy as noted above that prevents further administration of treatment
 - Recurrent Grade 2 pneumonitis
 - A confirmed positive serum pregnancy test
 - Noncompliance with trial treatment or procedure requirements
 - Investigator's decision to withdraw the subject

For subjects who are discontinued from treatment but continue to be monitored in the trial, all visits and procedures, as outlined in the trial flowchart, should be completed.

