- a. In subjects who discontinue study therapy without documented disease progression, every effort should be made to continue monitoring their disease status by radiologic imaging every 12 weeks (\pm 7 days) until (1) the start of new anti-cancer treatment, (2) documented disease progression by investigator assessment, (3) death, or (4) the end of the study, whichever occurs first.
- b. After the start of new anti-cancer treatment or documented disease progression by investigator assessment, the subject will transition to the Survival Follow-up and should be contacted by telephone (or in person if recent contact for other purposes during window) approximately every 12 weeks to assess survival status. Updated survival status may be requested by the Sponsor at any time during the course of the study. Upon Sponsor notification, all subjects who do not/will not have a scheduled study visit or study contact during the Sponsor-defined time period will be contacted for their survival status (excluding subjects who have a death event previously recorded).
- c. If subjects have stable disease, partial remission, or complete response they should continue on every 12 week (\pm 7 days) assessment schedule as described in section 7.1.2.7.4. Imaging should occur at any time where there is clinical suspicion of progression.
- d. In subjects with an unconfirmed PD assessment who continued study therapy, a radiological assessment should be performed 12 weeks (\pm 7 days) later or at the time of treatment discontinuation. If previous scan was obtained within 4 weeks prior to the date of discontinuation, then a repeat scan at treatment discontinuation isn't mandatory. However, imaging should occur at any time where there is clinical suspicion of progression.
- e. For women of reproductive potential, a urine pregnancy test should be performed within 72 hours prior to each cycle of trial treatment. If urine pregnancy results cannot be confirmed as negative, a serum pregnancy test performed by the local study site laboratory will be required. Pregnancy tests (serum and/or urine tests) should be repeated if required by local guidelines.

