8.6.1.3 Progression-Free Survival

The non-parametric Kaplan-Meier method will be used to estimate the PFS curve.

Since disease progression is assessed periodically, PD can occur any time in the time interval between the last assessment where PD was not documented and the assessment when PD is documented. For the primary analysis, for the subjects who have PD, the true date of disease progression will be approximated by the date of the first assessment at which PD is objectively documented per IWG criteria, regardless of discontinuation of study drug. Death is always considered as a confirmed PD event.

In order to evaluate the robustness of the PFS endpoint, we will perform two sensitivity analyses with a different set of censoring rules. The first sensitivity analysis is the same as the primary analysis except that it censors at the last disease assessment without PD when PD or death is documented after more than one missed disease assessment. The second sensitivity analysis is the same as the primary analysis except that it considers discontinuation of treatment or initiation of new anticancer treatment, whichever occurs later, to be a PD event for subjects without documented PD or death. The censoring rules for primary and sensitivity analyses are summarized in [Table 9](#).

Table 9 Censoring rules for Primary and Sensitivity Analyses of Progression-Free Survival

Situation	Primary Analysis	Sensitivity Analysis 1	Sensitivity Analysis 2
No progressive disease (PD) and no death; new anticancer treatment is not initiated	Censored at last disease assessment	Censored at last disease assessment	Censored at last disease assessment
No PD and no death; new anticancer treatment is initiated	Censored at last disease assessment before new anticancer treatment	Censored at last disease assessment before new anticancer treatment	Progressed at date of new anticancer treatment
PD or death documented after ≤ 1 missed disease assessment	Progressed at date of documented PD or death	Progressed at date of documented PD or death	Progressed at date of documented PD or death
PD or death documented after ≥ 2 missed disease assessments	Progressed at date of documented PD or death	Censored at last disease assessment prior to the ≥ 2 missed disease assessment	Progressed at date of documented PD or death

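### In the rrRS cohort, CLL drugs may be added during pembrolizumab under conflicting rules, and the ORR definition has no rule for them, so the rrRS ORR may not be the ORR of pembrolizumab alone

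*Combined protocol and SAP*

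**What the plan says.** Section 3.1 gives the second primary objective as "rrRS: Estimate the ORR of pembrolizumab by independent central review". It is an estimation objective with no hypothesis test.

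Section 2.1 says that in rrRS subjects CLL therapies "may be added (Section 5.5.1) at the physician's discretion if medically necessary and with Sponsor approval". Section 5.5.1 repeats the permission ("additional therapies to treat the underlying CLL (according to treatment guidelines) may be added") and limits it to commercially available drugs approved for CLL.

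Other sections point elsewhere:

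- Section 5.5.2 lists "Antineoplastic systemic chemotherapy or biological therapy" as prohibited in the screening and treatment phases. It writes exceptions for immunoglobulin and some radiation, but none for CLL in rrRS. Subjects who "require the use of any of the aforementioned treatments for clinical management should be removed from the trial".
- Section 5.8.1 makes this a reason for mandatory discontinuation of treatment: "Any progression or recurrence of any malignancy, or any occurrence of another malignancy that requires active treatment". Exclusion criterion 6 excepts underlying CLL; this bullet does not.
- Section 6.1, footnote b: "After the start of new anti-cancer treatment or documented disease progression by investigator assessment, the subject will transition to the Survival Follow-up". Section 7.1.2.7.4 likewise ends disease assessments when new anti-cancer treatment starts.

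On the endpoints, Sections 8.4.1 and 8.6.1.1 count a CR or PR whenever it occurs in the study, provided it precedes progression. They do not mention added therapy. For PFS without progression or death, Table 9 prescribes "Censored at last disease assessment before new anticancer treatment" in the primary analysis. Section 8.6.1.4 censors DOR when a subject receives antitumor treatment other than study treatment.

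**The concern.** Eligibility requires RS that transformed from CLL, so the permission could apply to anyone in the cohort. Two things are at stake.

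First, the meaning of a primary estimate. If a subject starts a CLL drug, stays on pembrolizumab, keeps being scanned and then reaches a first CR or PR, the ORR definition credits that response to the trial treatment. The objective names only pembrolizumab.

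Second, consistency of conduct and of endpoints. Depending on which section is followed, a subject whose CLL needs treatment might stay on treatment with scans, be removed from the trial, or stop treatment and be followed for survival only. The same clinical event then gives different ORR, PFS and DOR records.

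**Working it through.** **Does a response after an added CLL drug count?** The plan never says whether a permitted CLL drug is new anti-cancer treatment, so both readings need following.

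| | CLL drug is new anti-cancer treatment | CLL drug is not |
|---|---|---|
| Imaging (7.1.2.7.4, footnote b) | stops | continues |
| A later first CR/PR | would not be observed on schedule | observed, and counts in ORR |
| PFS, no progression or death (Table 9) | censored before the drug | not censored for it |
| DOR (8.6.1.4) | censored | on its face still censored, since the drug is antitumor treatment other than study treatment |

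The second column fits better with Section 5.5.1, which treats the drug as an acceptable concomitant medication. It also fits Section 7.1.1.5.4, which moves subjects to survival follow-up for new therapy begun after the last trial dose. No section settles it.

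**How far does the prohibition reach?** Section 5.5.2 names chemotherapy, biologics and immunotherapy, but not targeted small molecules. However, Section 5.5 carries drugs prohibited by the exclusion criteria into the trial period. Exclusion criterion 4 names targeted small molecules, and its ibrutinib exception for rrRS covers only the time up to 24 hours before the first dose. The conflict with 5.5.1 is therefore direct for chemotherapy and biologics, and arises through Section 5.5 for small molecules.

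**The plan's own precision figure.** Section 8.8 gives a maximum half-width of 12% for the exact 90% interval at n = 50. Clopper-Pearson limits are 19.5–42.4% for 15/50, 37.6–62.4% for 25/50 and 57.6–80.5% for 35/50. All match Table 12 after rounding. The maximum half-width is 12.4%, so the figure reproduces. At the 24 subjects enrolled (Section 2.1) it is 18.1%.

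**Size per subject.** Each response recounted as a non-response moves the ORR by 1/n:

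- n = 24: 1/24 = 4.2 points; three subjects, 3/24 = 12.5 points.
- n = 50 (planned): 1/50 = 2.0 points.
- If 6% of the 24 were untreated, as Section 8.8 assumes, about 24 × 0.94 ≈ 23 remain, and 1/23 = 4.3 points.

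**Illustration.** Assume 7 responders among 24, of whom k first responded after an added CLL drug. Both numbers are assumptions.

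| k | ORR counting them as non-responders | exact 90% CI |
|---|---|---|
| 0 | 7/24 = 29.2% | 14.6–47.9% |
| 1 | 6/24 = 25.0% | 11.5–43.5% |
| 2 | 5/24 = 20.8% | 8.6–38.9% |
| 3 | 4/24 = 16.7% | 5.9–34.2% |

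**Expected shift.** If a fraction f of subjects receive CLL therapy before response, and it raises their response probability by d, the upward shift is f × d. Assumed values give 5% × 20 points = 1 point, 20% × 30 points = 6 points, and 30% × 50 points = 15 points.

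**The case against.** The strongest case on the other side has five parts.

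- **Sponsor control.** Adding a CLL drug needs Sponsor approval, removal under 5.5.2 follows Sponsor consultation, and continuation under 5.5 needs Sponsor agreement. Sites are not choosing freely. This stands as to conduct, but approval governs access to the drug and not how the response is counted.
- **The specific rule may override the general ones.** Read with full literalness, the any-malignancy bullet in 5.8.1 would also defeat the bullet in the same list that allows Sponsor-approved treatment after confirmed progression. It was probably not meant that way. That softens the conflict, but the text still lacks the CLL exception that the eligibility criteria contain.
- **Later responses may not count at all.** A reader might infer that the plan counts every response after an added CLL drug. It does so only if imaging continues. If the drug is new anti-cancer treatment, scheduled imaging ends. This stands, and the conclusion is conditional for that reason.
- **DOR is largely covered.** The wording of 8.6.1.4 already reaches an added CLL drug. This stands; the open question is mainly PFS.
- **The objective does not say single agent for rrRS.** That phrase appears only in the rrPMBCL hypothesis. Whether permitted CLL therapy belongs to what is estimated is a legitimate choice, but the plan does not state it.

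A reader might also infer that shrinkage of CLL nodes under the added drug would itself be scored as PR. Section 12.7 separates RS from CLL in marrow and for residual disease at CR, and gives no such rule for nodal size at PR, so this is possible. But rrRS subjects must have a PET-positive lesion at screening, Section 7.1.2.7.1 advises considering node biopsy for enlarging nodes, and Section 12.7 refers to an imaging charter for further detail. It cannot be asserted from these documents.

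**Conclusion.** The point holds in conditional form. The permission in 2.1 and 5.5.1 is not reconciled with 5.5.2, 5.8.1, 7.1.2.7.4 and footnote b, and the ORR definition has no rule for added CLL therapy. If imaging continues after such therapy, the rrRS ORR may not be the ORR of pembrolizumab alone.

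The stronger statement, that it is not the ORR of pembrolizumab, is not supported. The estimate departs only through subjects whose first response follows an added CLL drug. Their number is not in the documents and may be zero, in which case nothing changes. The 4.2 points per subject is also an upper bound on what the CLL drug contributed, because some of these subjects might have responded to pembrolizumab alone.

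The reach is limited to an estimation-only cohort closed after 24 subjects. The rrPMBCL hypothesis test and its boundaries are unaffected. Because the estimate serves a primary objective and the remedy is cheap, the change is worth making.

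**What to change.** 1. In 8.6.1.1, for rrRS, keep the ORR as defined and add a sensitivity ORR in which a subject whose first CR or PR is documented after added CLL therapy is a non-responder. Report both, with the number of rrRS subjects who received such therapy and when. A sensitivity analysis is preferable to a new primary definition: the cohort is open-label and its enrollment had ended by Amendment 04, so redefining the primary endpoint would be post hoc.
2. In Table 9, state whether added CLL therapy is new anticancer treatment for rrRS PFS. Apply the same rule to DOR, where 8.6.1.4 already censors for other antitumor treatment.
3. Reconcile 5.5, 5.5.1, 5.5.2, 5.8.1, 7.1.2.7.4 and flow chart footnote b so that one rule applies when CLL therapy is started. Which rule is for the sponsor's clinicians.

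Cost: some wording, one additional analysis and a possibly lower sensitivity ORR. Section 8.0 already allows rrRS analyses to be modified and reported in the study report. Start dates of added CLL therapy must be confirmed as recorded, because 5.5.1 makes date documentation for medication changes on the CRF optional, and the sensitivity analysis depends on them.
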